## 10.5 Timing of Patient's Visits to the Clinic

Patients will be asked to report to the clinic for their scheduled appointments. If a subject is unable to schedule an appointment within the required time frame, study staff will be asked to reschedule the patient to a day when they are able to come in within a predetermined time frame.

## 10.6 Description by Type of Visit

## 10.6.1 Screening Visit (V1; Study Day -29) (-42 to -28 days visit window)

- informed consent completed and signed
- inclusion and exclusion criteria
- demographic data
- medical/surgical history
- smoking status
- record concomitant medications
- obtain in clinic blood pressure, heart rate, respiratory rate
- brief physical exam
- neurological exam
- body weight
- height measurement
- 12-lead ECG
- nasal inspection
- laboratory testing (blood for metabolic panel, hematology, clinical chemistry, lipid panel, liver function test, urinalysis)
- urine pregnancy test (for women of childbearing potential)
- study AEs
- study diary
- migraine pain intensity score

# 10.6.2 Baseline (Beginning of 4 Week Baseline Period) (V2; Study Day -28) (-31 to -27 Days Visit Window)

- inclusion and exclusion criteria
- record concomitant medications
- obtain in clinic blood pressure, heart rate, respiratory rate
- brief physical exam
- neurological exam
- · body weight
- nasal inspection
- study AEs
- study diary
- migraine pain intensity score
- MIDAS
- HIT-6
- MSQL
- CGI

# 10.6.3 Randomization (End of 4 Week Baseline Period) (V3; Study Day 0) (±3 Days Visit Window)

- inclusion and exclusion criteria, including entry criteria of 4-14 migraine headache days during the baseline period
- record concomitant medications
- obtain in clinic blood pressure, heart rate, respiratory rate
- brief physical exam
- neurological exam
- body weight
- blood collection for biomarkers
- 12-lead ECG
- allocation of a randomized treatment kit number via randomization system
- nasal inspection
- delivery of the corresponding pack of Investigational Product
- Investigational Product application
- obtain study medication weight for Investigational Product compliance
- study counseling
- laboratory testing (blood for metabolic panel, hematology, clinical chemistry, lipid panel, liver function test, urinalysis)
- nasal fluid collection for biomarkers
- study AEs
- study diary
- migraine pain intensity score
- MIDAS

- HIT-6
- MSQL
- CGI

## 10.6.4 Prevention Treatment Week 4 (V4; Study Day 28) (±3 Days Visit Window)

- record concomitant medications
- obtain in clinic blood pressure, heart rate, respiratory rate
- brief physical exam
- neurological exam
- body weight
- blood collection for biomarkers
- nasal inspection
- Investigational Product application
- obtain study medication weight for Investigational Product compliance
- study counseling
- nasal fluid collection for biomarkers
- study AEs
- study diary
- migraine pain intensity score
- HIT-6
- MSQL
- CGI

## 10.6.5 Prevention Treatment Week 8 (V5; Study Day 56) (±3 Days Visit Window)

- record concomitant medications
- obtain in clinic blood pressure, heart rate, respiratory rate
- brief physical exam
- · neurological exam
- body weight
- blood collection for biomarkers
- nasal inspection
- Investigational Product application
- obtain study medication weight for Investigational Product compliance
- study counseling
- nasal fluid collection for biomarkers
- study AEs
- study diary
- migraine pain intensity score
- HIT-6
- MSQL
- CGI

## 10.6.6 Prevention Treatment Week 12 (V6; Study Day 84) (±3 Days Visit Window)

- record concomitant medications
- obtain in clinic blood pressure, heart rate, respiratory rate
- brief physical exam
- neurological exam
- body weight
- blood collection for biomarkers
- 12-lead ECG
- nasal inspection
- Investigational Product application
- obtain study medication weight for Investigational Product compliance
- laboratory testing (blood for metabolic panel, hematology, clinical chemistry, lipid panel, liver function test, urinalysis)
- nasal fluid collection for biomarkers
- study AEs
- study diary
- migraine pain intensity score
- MIDAS
- HIT-6
- MSOL
- CGI

## 10.6.7 Follow-Up Week 16 (End of Study) (V7; Study Day 112) (±3 Days Visit Window)

Every attempt should be made to complete all visits during the defined window periods. Subjects who do not complete all required study visits and withdraw from the study will be asked to complete an End of Study Evaluation.

- record concomitant medications
- · obtain in clinic blood pressure, heart rate, respiratory rate
- brief physical exam
- neurological exam
- body weight
- blood collection for biomarkers
- nasal inspection
- nasal fluid collection for biomarkers
- study AEs
- study diary
- migraine pain intensity score
- HIT-6
- MSQL
- CGI
- subject satisfaction survey

## 10.6.8 Unscheduled/Unanticipated or Early Termination Study Visit

If an event arises that requires patient to come in to the research center, subjects should be scheduled for the Unscheduled visit.

During the visit, the following will be obtained:

- · record concomitant medications
- obtain in clinic blood pressure, heart rate, respiratory rate
- brief physical exam
- neurological exam
- body weight
- blood collection for biomarkers
- nasal inspection
- obtain study medication weight for Investigational Product compliance
- study counseling
- laboratory testing (blood for metabolic panel, hematology, clinical chemistry, lipid panel, liver function test, urinalysis)
- nasal fluid collection for biomarkers
- study AEs
- study diary
- migraine pain intensity score
- MIDAS
- HIT-6
- MSQL
- CGI

#### 11 METHODS OF ASSESSMENTS

#### 11.1 Blood Pressure Measurement

Blood pressure readings will be obtained at every visit as described in Appendix A (schedule of events) preferably during standardized times across sites (e.g., mornings). Subject should be asked to remove all clothing that covers the location of cuff placement. The individual should be comfortably seated in the chair, with the legs uncrossed, and the back and arm supported, such that the middle of the cuff on the upper arm is at the level of the right atrium (the mid-point of the sternum). Neither the patient nor the observer should talk during the measurement. After 5 minutes sitting, serial clinic BP measurements and heart (x3) rate will be performed, using the non-dominant arm with a calibrated electronic sphygmomanometer. The average of the second and third readings will be documented. Respiratory rate (number of breaths per minute) will also be recorded.

## 11.2 Brief Physical Examinations

Brief physical examination will be performed at Screening (V1), Baseline (beginning of 4 week baseline period; V2), Randomization (end of 4 week baseline period; V3), Prevention Treatment

Week 4 (V4), Prevention Treatment Week 8 (V5), Prevention Treatment Week 12 (V6), Follow-Up Week 16 (End of Study; V7), and at Unanticipated/Early Termination Visit should one occur. The physical examination includes an assessment of general appearance and a review of systems (dermatologic, head, eyes, ears, nose, mouth/throat/neck, thyroid, lymph nodes, respiratory, cardiovascular, gastrointestinal, extremities, musculoskeletal, neurologic systems).

## 11.3 Neurological Examinations

As part of the physical examination at each visit, a neurological examination will be performed for assessment of sensory neuron and motor responses, especially reflexes, to determine whether the nervous system is impaired.

#### 11.4 Blood Collection for Biomarkers

In addition to the blood drawn for the safety laboratory assessments, additional whole blood will be collected for the biomarker analysis at Randomization (end of 4 week baseline period; V3), Prevention Treatment Week 4 (V4), Prevention Treatment Week 8 (V5), Prevention Treatment Week 12 (V6), and Follow-Up Week 16 (End of Study; V7) according to Appendix A. Samples will also be collected in the event of an Unanticipated/Early Termination Visit.

Approximately 15 ml of whole blood will be drawn for biomarkers at each visit. Patients will be asked to fast for at least 8 hrs before blood for biomarkers is drawn.

Samples will be processed to serum and plasma on site and stored at -80 C until shipment to a designated central lab for biostorage and may be evaluated for select biomarkers that may include several of the following as well as others:

1. Inflammatory cytokines/chemokines/immune cell markers/neuropeptides: IL-1beta, IL-2, IL-4, IL-5, IL-6, IL-8, IL-9, IL-10, IL-12p40, IL-12p70, IL-13, IL-15, IL-16, IL-17, IL-18, TNF-alpha, GM-CSF, MIP-1 alpha, MIP-1 beta, MCP-1, Eotaxin-1, MDC, PGD2, beta-tryptase, histamine, C3a/C4a/C5a, LTC4, MMP9, CGRP

#### 11.5 12-Lead ECG

12-lead ECG will be taken at Screening (V1), Randomization (end of 4 week baseline period; V3), and Prevention Treatment Week 12 (V6). Standard 12-lead ECGs will be performed according to the site SOPs. ECGs should be performed after the subject has been resting supine for 5 minutes. The ECG will include all 12 standard leads and a Lead II rhythm strip on the bottom of the tracing. The ECG will be recorded at a paper speed of 25 mm/sec. The following ECG parameters will be collected: PR interval, QRS interval, QT interval, and QTc interval (QTcB; Bazetts correction). All ECGs must presence of abnormalities.

## 11.6 Nasal Inspection

Nasal inspection will include clinical examination of the nasal mucosa, sinuses, and upper airway using an otoscope. Nasal inspection will be performed at the following visits: Screening

b e

(V1), Baseline (beginning of 4 week baseline period; V2), Randomization (end of 4 week baseline period; V3), Prevention Treatment Week 4 (V4), Prevention Treatment Week 8 (V5), Prevention Treatment Week 12 (V6), Follow-Up Week 16 (End of Study; V7), and at Unanticipated/Early Termination Visit should one occur.

### 11.7 Laboratory Assessments

Blood sample will be taken for hematology and clinical chemistry, including standard metabolic panel, complete blood count (CBC), clinical chemistry, lipid panel, and liver function test. Approximately 15 ml of whole blood will be drawn. Urinalysis will be performed as part of safety labs. Laboratory assessments will be made at Screening (V1), Randomization (end of 4 week baseline period; V3), Prevention Treatment Week 12 (V6), and at Unanticipated/Early Termination Visit should one occur.

Blood samples should be taken using standard venipuncture techniques. Blood sampling will be performed according to the site SOPs.

The following laboratory variables will be determined: Fasting glucose, Uric acid, BUN (blood urea nitrogen), Creatinine, BUN/creatinine ratio, eGFR (estimated glomerular filtration rate), Sodium, Potassium, Chloride, Calcium, Total protein, Bicarbonate, Albumin, Bilirubin, Alkaline phosphatase, AST (aspartate aminotransferase), ALT (alanine transaminase), total cholesterol, HDL, LDL, triglycerides, CBC (standard panel including RBC, hemoglobin, hematocrit, platelets, and WBC, including neutrophils, lymphocytes, monocytes, eosinophils, basophils), and proteinurea.

Any value outside the normal range (except those affected by not fasting) will be flagged for the attention of the Investigator or designee at the site. The Investigator or designee will indicate whether or not the value is of clinical significance. If the result of the clinical chemistry test from the samples taken during the screening phase is indicated as clinically significant, the study subject will NOT be allowed into the study.

#### 11.8 Urine Pregnancy Test

Standard urine pregnancy testing will be performed on WOCBP as part of screening.

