## 7.2 Screening for Eligibility

Informed consent will be obtained prior to any screening assessments. Screening assessments (Visit 1; V1) will be performed within 2 weeks (-14 days) prior to the Baseline visit (V2) and will include: medical history and medication use, complete physical examination including height, weight, vital signs, and 12-lead ECG, a neurological examination, nasal inspection, laboratory testing, including blood sample for a comprehensive metabolic panel, complete blood count, chemistry, lipid panel, and liver function test, as well as urinalysis. Urine pregnancy test will be performed on WOCBP. All screening evaluations must be completed and reviewed to confirm that participants meet all eligibility criteria before entering baseline period on Day -28. Inclusion and exclusion criteria will be reviewed at Screening (V1), Baseline visit (V2), and Randomization visit (V3) to make sure nothing changed. Enrolled subjects will be asked to undergo a 4 week (Day -28 to 0) baseline period.

Eligible subjects will return to clinic on Day -28 (V2) for baseline assessments and will be sent home to record their migraine events and acute migraine medication use over the 28 day baseline period using a diary. Subjects will return to clinic on Day 0 (V3) for randomization upon confirming continued eligibility. Subjects are randomized at V3 upon confirming the inclusion/exclusion criteria and the entry criteria of 4-14 migraine headache days and 80% diary compliance during the baseline period.

For subjects who do not meet the 80% daily diary compliance but otherwise meet the 4-14 migraine days requirement during the baseline period, they can be provided additional opportunities to meet the 80% diary compliance requirement to enable continued eligibility for randomization. The following allowances can be made per investigator judgement on a case by case basis:

- If the anticipated diary compliance is slightly less than 80% or short by 4 daily diary entries by the day before the randomization visit, subjects can enter up to 4 additional days of diary entries (over the ±3 day visit window specified in the schedule of events in the protocol) as part of the baseline period and reschedule the randomization visit immediately after this period. This provides up to 7 additional days of diary entries to fulfill compliance. Twenty-eight days prior to the new randomization visit day can be re-evaluated for the baseline period.

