## 10.3 Study Assessments

Study activities will take place according to the Schedule of Events table (Appendix A).

All subjects will attend a screening visit (V1) not more than 14 days prior to V2 (Day -28). Subjects with a history of migraine as defined in the inclusion/exclusion criteria who pass screening will return to clinic on Day -28 (V2) for baseline assessments and sent home to record their migraine events and rescue (acute migraine treatment) medications over the 28 day baseline period using a diary. Subjects will return to clinic on Day 0 (V3) to determine continued study eligibility. Subjects who continue to meet all inclusion and exclusion criteria will be randomized to receive study treatment.

Subjects will then be trained for in-home treatment/assessment on the use of the nasal spray, and apply their first dose of treatment under the supervision of study personnel while on site (V3). Subjects will remain onsite for 1 hour post dosing for observation. Subjects will then be dispensed study medication for 12 weeks of at home dosing (either 1x10^9 cell/ml; 4x10^9 cells/ml; or vehicle). While at home, subjects will dose twice daily (am and pm) for 12 weeks during the prevention treatment phase, starting with the second dose of the first day of treatment.

Subjects will record their dosing, migraine events, and rescue medications daily and return to clinic every 4 weeks during the 12 week treatment period at Day 28 (V4), Day 56 (V5), and Day 84 (V6) for safety and additional prevention treatment assessments. Additional safety assessments will be made during the 28 day follow-up period and end of study visit at Day 112 (V7).

At the final visit (V7) or at the Early Termination visit due to study discontinuation or withdrawal, subjects may be requested to complete an optional, brief subject satisfaction survey.

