# 27 APPENDIX A-SCHEDULE OF EVENTS

Visit name (Day)	Screening	Baseline (Beginning of 4 week baseline period)	Randomization (End of 4 week baseline period)	Prevention Treatment Week 4	Prevention Treatment Week 8	Prevention Treatment Week 12	Follow-Up (End of Study) Week 16	Unanticipated/Early Termination Visit
Visit	V1 (Day -29)	V2 (Day -28)	V3 (Day 0)	V4 (Day 28)	V5 (Day 56)	V6 (Day 84)	V7 (Day 112)	
Visit Window, in Days	-42 to -28	-31 to -27	±3	±3	±3	±3	±3	
Informed Consent 	X							
Inclusion/Exclusion Criteria 		X	$X^{17}$					
Demographics								
Medical history								
Smoking status								
Concomitant medications		X	X	X	X	X	X	
Vital signs (HR, BP, respiratory rate)	X		X	X	X	X	X	
Brief Physical exam	X	X	X	X	X	X	X	

Neurological exam	X	X	X	X	X	X	X	X
Body weight	X	X	X	X	X	X	X	
Height	X							
Blood collection 			X	X	X	X	X	X
12-lead ECG	X		X			X		
Randomization 			X					
Nasal inspection 	X	X	X	X	X	X	X	X
Delivery of Investigational Product			X					
Investigational Product application 			X	X	X	X		
Investigational Product compliance 			X	X	X	X		X
Counseling 			X	X	X			X
Laboratory testing 	X		X			X		X
Urinary pregnancy test 	X							
Nasal fluid 			X	X	X	X	X	X
Safety AEs	X	X	X	X	X	X	X	X

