## CONFIDENTIAL

Study diary 	X	X	X	X	X	X	X	X
Migraine pain intensity score	X	X	X	X	X	X	X	X
MIDAS 		X	X			X		X
HIT-6 		X	X	X	X	X	X	X
MSQL 		X	X	X	X	X	X	X
CGI 		X	X	X	X	X	X	X
Subject Satisfaction Survey							X	X 

- 1. Informed consent can be obtained up to 14 days prior to the baseline visit (V2).
- 2. Inclusion and exclusion criteria will be reviewed at Screening (V1), Baseline (V2), and Randomization (V3) visits to make sure nothing changed.
- 3. Blood samples for biomarkers will be collected and processed on site. Serum/plasma samples will be frozen onsite and shipped to the Central lab for storage.
- 4. Subject's demographic data and medical history are blinded to the statistician for randomization and treatment assignment. Only subjects with 4-14 migraine headache days per month during baseline period (28 days between V2 and V3) will be randomized.
- 5. Nasal inspection will include clinical examination of the nasal mucosa, sinuses, and upper airway using an otoscope.
- 6. Subjects will be trained for in-home treatment/assessment on the use of the nasal spray, and have their first dose of treatment on site (V3). Subjects will remain onsite for observation for 1 hour post dosing. Subjects will then be dispensed study medication for 12 weeks of at home dosing.
- 7. Weight of individual IP bottles will be obtained at visits V3 (before and after first dose), V4, V5, V6, and unanticipated/early termination visit.
- 8. Subjects will be counseled on the application of the nasal spray, study diary, and answer any questions.
- 9. Fasting blood sample for a comprehensive metabolic panel, complete blood count, chemistry, lipid panel, and liver function test-15 ml. Also includes urinalysis. Patients should fast for at least 8 hours before the test. Blood will be shipped to the central lab for processing.
- 10. Urine pregnancy test to be done on WOCBP.
- 11. Intranasal strip will be used to collect nasal fluid for inflammatory cytokines. Optionally, nasal fluid may be evaluated for nasal microbiome (e.g., PCR) to confirm presence of B244.

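### The only scheduled pregnancy test is at screening (V1), nominally 29 days before the first dose at V3, and no repeat test is required at V3

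*Protocol*

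**What the plan says.** Four places in the protocol put the urine pregnancy test at screening: sections 7.2, 10.6.1 and 11.8, and the Schedule of Events in Appendix A. Section 11.8 reads: "Standard urine pregnancy testing will be performed on WOCBP as part of screening". Section 10.6.1 includes it in the V1 visit list as "urine pregnancy test (for women of childbearing potential". Appendix A has one mark for it, in the V1 column, and note 10 only says "Urine pregnancy test to be done on WOCBP". The visit lists for V2 to V7 and for the unscheduled or early termination visit (10.6.2 to 10.6.8) do not include it. The laboratory variables in section 11.7 contain no hCG.

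Section 7.2 requires screening evaluations to be complete and reviewed before the baseline period starts on Day -28. Pregnancy and breast-feeding are exclusion 12, and not using adequate contraception is exclusion 13. The criteria are looked at again later: "Inclusion and exclusion criteria will be reviewed at Screening (V1), Baseline visit (V2), and Randomization visit (V3) to make sure nothing changed". Section 12.3 keeps out participants who report pregnancy during that review.

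At V3, participants are randomised and then "apply their first dose of treatment under the supervision of study personnel while on site (V3". The V3 list in section 10.6.3 includes "laboratory testing (blood for metabolic panel, hematology, clinical chemistry, lipid panel, liver function test, urinalysis", so urine is already collected at that visit.

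**The concern.** The protocol accepts that eligibility can change during baseline. At V3 it repeats the criteria review, vital signs, examinations, ECG, nasal inspection and the safety laboratory panel. Pregnancy is an exclusion in its own right, yet its one objective check is not repeated. A test at V1 cannot detect a conception that happens after V1, and a woman who does not know she is pregnant cannot report it.

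What is at stake is participant safety. A woman who meets exclusion 12 without knowing it could be randomised and start 12 weeks of twice-daily dosing, and no later test is scheduled that would reveal the pregnancy. Section 9, in what male participants must tell their partners, describes the effects on a fetus and on a pregnant woman as unknown. The sample size and the analyses are not touched.

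**Working it through.** **Inputs from the protocol**

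- V1: nominal Day -29, window Day -42 to Day -28 (10.6.1, Appendix A).
- V3: nominal Day 0, window ±3 days (10.6.3, Appendix A). Randomisation and first dose take place here (10.3).
- Diary allowance: up to 4 days beyond the V3 window (7.2).
- Repeated baseline: 28 further diary days (7.2).
- Reset baseline: no number of days stated (7.2).
- V7: Day 112. Planned duration per subject: up to 22 weeks (Clinical Trial Summary).

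**Gap from the only test to the first dose** (day of V3 minus day of V1)

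| Case | Arithmetic | Days |
|---|---|---|
| Nominal | 0 - (-29) | 29 |
| Shortest by windows | -3 - (-28) | 25 |
| Longest by windows | 3 - (-42) | 45 |
| With the 4-day allowance | (3 + 4) - (-42) | 49 |
| One repeated baseline, nominal dates | 29 + 28 | 57 |

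**Check against the planned duration**

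- The protocol's own figure reproduces: Day -42 to Day 112 is 42 + 112 = 154 days, and 154 / 7 = 22 weeks. That plan leaves 154 - 112 = 42 days from V1 to V3.
- One repeated baseline gives 57 + 112 = 169 days, or 24.1 weeks, which is over the planned figure.
- The visit windows alone can also pass it slightly. With V7 counted 112 days after the actual V3, 45 + 112 = 157 days, or 22.4 weeks. The 22 weeks is therefore a planning figure. It does not cancel the reset and repeat options that section 7.2 grants explicitly.

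**What has to be shown at V3**

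- Section 7.2 sets the conditions for randomisation as the inclusion and exclusion criteria, 4 to 14 migraine days and 80% diary compliance. A pregnancy test is not among them.
- Section 12.3 frames the pregnancy check before randomisation as what the participant reports.
- None of the diary allowances in 7.2 (extension, reset or repeat) carries a retest.

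The protocol gives no expected number of pregnancies, so days of gap are the only size that can be computed. They describe the schedule and are not a risk estimate.

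**The case against.** The strongest reply is that pregnancy is already handled in layers: a test at V1, exclusions 12 and 13 reviewed again at V2 and V3, required contraception with at least 90 days on the same pill for oral users, exclusion of women who report pregnancy, and product stopped with follow-up to outcome once a pregnancy is known. Section 20 also lets an investigator add a safety assessment case by case. This stands as far as it goes, and it is why few cases are expected. But the contraception rules lower the chance of pregnancy without detecting one, and section 20 permits a test without requiring it.

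A reader might infer several stronger things that the document does not support:

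- *That no negative test is needed at all before dosing.* Exclusion 12, with the review of screening results required by 7.2, means that a positive V1 test bars entry. Only a repeat at V3 is missing.
- *That the gap is open-ended.* Section 7.2 states no cap on a reset, but the planned duration of up to 22 weeks leaves about 42 days from V1 to V3. Longer gaps are case-by-case exceptions for subjects short of 80% diary compliance.
- *That the protocol contradicts itself.* All the sections agree on V1.
- *That the product is a known hazard in pregnancy.* The introduction cites no reported health risks from topical use or ingestion of the genus, and a 28-day intranasal rat study found safe and well tolerated. These are not reproductive data, so the unknown in section 9 remains, but no hazard is shown.

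**Conclusion.** The point holds as a weak schedule, not as an error or a contradiction. The only scheduled test precedes the first dose by 29 days nominally, 25 to 45 days by the visit windows and up to 49 days with the diary allowance. One repeated baseline would make it 57 days, beyond the planned duration. A negative V1 result is implied, but nothing at V3 can reveal a pregnancy that began after V1 and is not yet recognised.

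The day counts rest on the visit days and windows as printed. That few pregnancies would be affected is a judgement from the contraception requirements, because the protocol gives no figure. No analysis, endpoint or sample size changes. The repeat test should be added because it is cheap and closes a gap that contraception rules and self-report cannot.

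**What to change.** Require a negative urine pregnancy test, read on site, for every woman of childbearing potential at V3 before randomisation and first dose. Collect the urine before the kit is allocated. V3 already includes urinalysis, but section 10.6.3 lists laboratory testing after kit allocation and product application and does not say whether that order is chronological, so the order should be stated. The test must be read on site because section 11.16 ships laboratory samples overnight to the central laboratory.

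Places to edit:

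- 7.2: add the negative V3 test to the conditions for randomisation.
- 10.6.3: add the test to the visit list, ahead of kit allocation.
- 11.8: place testing *at screening (V1) and at V3 before randomisation*.
- 12.3: extend the bar on randomisation to *any participant whose V3 urine pregnancy test is positive*.
- Appendix A: mark the V3 column.

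Because the test is tied to V3 itself, it also covers an extended, reset or repeated baseline.

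Cost: test kits (about 303 at most if each planned subject were tested once, and fewer because only women of childbearing potential need one), a few minutes' wait, and a protocol amendment with IRB approval under section 26, possibly with a consent-form change.
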